9.2.3. Adverse Event Summaries

Overall summaries of TEAEs by treatment regimen will be provided during the INCB050465 initial QD dosing period, maintenance dosing period, and overall period (ie, all TEAEs regardless of the timing of occurrence). These summaries will include the following:

- Number (%) of participants reporting any TEAEs
- Number (%) of participants reporting any Grade 3 or higher TEAEs
- Number (%) of participants reporting any serious TEAEs
- Number (%) of participants reporting any TEAEs related to INCB050465
- Number (%) of participants reporting any Grade 3 or higher TEAEs related to INCB050465
- Number (%) of participants reporting any serious TEAEs related to INCB050465
- Number (%) of participants who had TEAE with fatal outcome
- Number (%) of participants with INCB050465 dose reductions because of TEAEs
- Number (%) of participants who temporarily interrupted INCB050465 because of TEAEs
- Number (%) of participants who permanently discontinued INCB050465 because of TEAEs

The following summaries will be produced for TEAEs during the overall period by MedDRA term (if 10 or fewer participants appear in a table, a listing may be appropriate):

- Summary of TEAEs by SOC and PT
- Summary of TEAEs by PT in decreasing order of frequency
- Summary of TEAEs by SOC, PT, and maximum severity
- Summary of TEAEs by PT and maximum severity in decreasing order of frequency
- Summary of Grade 3 or higher TEAEs by SOC and PT
- Summary of Grade 3 or higher TEAEs by PT in decreasing order of frequency
- Summary of serious TEAEs by SOC and PT
- Summary of serious TEAEs by PT in descending order of frequency
- Summary of INCB050465 treatment-related TEAEs by SOC and PT
- Summary of INCB050465 treatment-related TEAEs by PT in decreasing order of frequency
- Summary of INCB050465 treatment-related TEAEs by SOC, PT, and maximum severity
- Summary of Grade 3 or higher INCB050465 treatment-related TEAEs by SOC and PT
- Summary of INCB050465 treatment-related serious TEAEs by SOC and PT
- Summary of TEAEs with a fatal outcome by SOC and PT
- Summary of TEAEs leading to INCB050465 dose reduction by SOC and PT
- Summary of TEAEs leading to INCB050465 dose interruption by SOC and PT
- Summary of TEAEs leading to discontinuation of INCB050465 by SOC and PT
- Summary of selected TEAEs of special interest by maximum severity
- Summary of time to onset of selected TEAEs of special interest
- Summary of time to onset of selected TEAEs of special interest: life-table method
- Summary of longest duration of selected TEAEs of special interest

The following supporting summaries will be produced for TEAEs during the INCB050465 initial QD dosing period and the maintenance dosing period by MedDRA term. For the supporting summaries during the maintenance dosing period, participants who cross over to the selected treatment regimen after the start of the maintenance dosing period will be summarized in a separate group (ie, Crossover):

- Summary of TEAEs by PT in decreasing order of frequency
- Summary of TEAEs by PT and maximum severity in decreasing order of frequency
- Summary of Grade 3 or higher TEAEs by PT in decreasing order of frequency

- Summary of serious TEAEs by PT in descending order of frequency
- Summary of TEAEs with a fatal outcome by SOC and PT
- Summary of TEAEs leading to discontinuation of INCB050465 by SOC and PT

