of treatment was 123 days (range: 7-690). Adverse events observed in $\geq 20\%$ of subjects were nausea (36%), diarrhea (35%), fatigue (31%), cough (24%), and vomiting (24%). New or worsening Grade ≥ 3 anemia, thrombocytopenia, and neutropenia occurred in 7%, 10%, and 19% of subjects, respectively. No Grade ≥ 3 nonhematological treatment-related AEs were reported in $\geq 10\%$ of subjects. Serious AEs that occurred in ≥ 2 subjects included diarrhea (n = 5); pyrexia (n = 4); colitis, hypotension, and sepsis (n = 3 each); pneumonia, exfoliative dermatitis, syncope, bacteremia, respiratory failure, bronchitis, urinary tract infection, and ventricular tachycardia (n = 2 each). Fourteen (19%) of the 72 subjects discontinued study treatment due to the following 14 AEs: diarrhea (n = 3); exfoliative dermatitis and colitis (n = 2 each); pneumonitis, rash, psoriasis, neutropenia, cytomegalovirus colitis, pleural effusion, and hypercalcemia (n = 1 each). All but 1 of these events occurred after the 9-week disease assessment. No liver function test abnormalities Grade > 1 were reported while subjects were receiving study treatment. No dose-limiting toxicities were identified, and the maximum tolerated dose was not reached.

As of 18 AUG 2017, 30 objective responses as reported by investigators were observed at doses ≥ 10 mg QD in 55 subjects with diffuse large B-cell lymphoma, FL, marginal zone lymphoma, and MCL. These results include 3 CR/CMR, 1 PR/PMR, and 1 SD in 5 ibrutinib-naïve subjects with MCL, and 1 CMR, 1 PMR, and 1 SD in 4 ibrutinib-experienced subjects with MCL. All of these objective responses occurred by the time of the 9-week disease assessment. At the time of the data cutoff, 5 of these subjects had been on study treatment at least 6 months, 4 of whom had been on study treatment at least 10 months. The longest duration of study treatment among subjects with MCL was approximately 76 weeks, with 4 subjects ongoing.

Pharmacokinetics analysis showed that the t_{max} is 0.5 to 1 hour, the terminal half-life is approximately 8 to 12 hours, and the exposure appeared to be dose-proportional between 5 mg QD and 45 mg QD at steady state. The pharmacodynamic analyses demonstrated robust and sustained pathway inhibition at all dose levels tested (Phillips et al 2016). Refer to the IB for further details.

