1.4. Study Rationale

Multiple agents have been approved in the United States and the EU for the treatment of mantle cell lymphoma. One of these agents, ibrutinib, is currently being evaluated in the first line in combination with bendamustine and rituximab, which could potentially create a relatively large population of subjects who have received ibrutinib. Despite the unprecedented response observed with a targeted agent, a retrospective study conducted on 114 patients treated with ibrutinib showed a median OS after cessation of ibrutinib of 2.9 months (95% CI, 1.6-4.9). The poor outcome for patients treated with ibrutinib demonstrates the need for new therapies in the post-ibrutinib setting (Martin et al 2016). INCB050465 has demonstrated promising activity in relapsed or refractory subjects with MCL (see Section 1.3). This study will evaluate INCB050465 for efficacy and safety in subjects with MCL who were previously treated with ibrutinib or who have not received any type of a BTK inhibitor.

All subjects will receive INCB050465 20 mg QD for 8 weeks followed by either 20 mg once weekly or 2.5 mg QD. Based on an *ex vivo* whole blood assay, the 20 mg QD dose provides exposure ranging from approximately 2-fold above the IC₉₀ at trough to 19-fold above the IC₉₀ at peak. Data as of 02 SEP 2016 showed that of the 11 NHL subjects that were administered 20 mg QD, 10 achieved an objective response at the time of first disease assessment (9 weeks). However, among all evaluable subjects with an objective response (n = 20), 7 subjects (35%) discontinued study treatment due to an AE. Consequently, after receiving 20 mg QD of INCB050465 for 8 weeks, subjects will receive either 20 mg once weekly (Treatment A) or 2.5 mg QD (Treatment B) of INCB050465.

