1.5. Potential Risks and Benefits of the Treatment Regimen

INCB050465 has effects on the immune system. Therefore, subjects in this study will be monitored closely for evidence of infections or new cancers, and study treatment administration will be discontinued if there is evidence of clinically significant infection or new cancer.

Pneumocystis jirovecii pneumonia has not been reported with the use of INCB050465 as monotherapy. However, PJP was reported for 1 subject administered INCB050465 in combination with pembrolizumab in Study INCB 39110-107 (NCT02646748). All subjects in Study INCB 50465-205 will receive PJP prophylaxis. Subjects will be asked to report all sulfa drug allergies, and those allergic to standard PJP prophylaxis with sulfonamide antibiotics will receive either inhaled pentamidine or atovaquone for PJP prophylaxis; these subjects will not be given dapsone.

As presented in Section 1.3, objective responses were reported in 30 of 55 NHL subjects, including 6 responses in 9 MCL subjects. Adverse events were also observed in subjects administered INCB050465 (see Section 1.3). Dose modification guidance and supportive care guidelines for diarrhea/colitis are implemented in this study. INCB050465 monotherapy has also demonstrated efficacy in multiple tumor types including MCL (see Section 1.3).

Based on safety and efficacy data from the ongoing Study INCB 50465-101, the treatment regimen for this study will be 20 mg QD for 8 weeks, followed by either 20 mg once weekly or 2.5 mg QD of INCB050465. As detailed in Section 1.3, these regimens are proposed to assess whether the frequency of AEs leading to treatment withdrawal will be reduced while maintaining PI3K pathway inhibition and maintenance of response.

INCB050465 is metabolized primarily by CYP3A4; therefore, use of any potent CYP3A4 inhibitors or inducers within 14 days or 5 half-lives (whichever is longer) before the first dose of INCB050465 will be prohibited.

The effects of INCB050465 on fetal development have not been evaluated, nor is it known whether INCB050465 passes into human breast milk; therefore, subjects who are pregnant or breastfeeding are excluded from participation in this study.

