5.4.4. Definition for Immune-Related Adverse Events

Adverse events of a potential immunologic etiology, or irAEs, may be defined as an AE consistent with an immune phenomenon associated with study treatment exposure after all other etiologies have been eliminated. Immune-related AEs may be expected based on previous experience with INCB050465. Special attention should be paid to AEs that may be suggestive of potential irAEs. Based on emerging data from the ongoing Study INCB 50465-101, most irAEs occur after the first 9 weeks of study treatment administration. However, an irAE could occur at any time. Suspected irAEs should be discussed with the medical monitor when possible.

Subjects should receive appropriate supportive care measures as deemed necessary by the treating investigator. Suggested supportive care measures for the management of drug-related AEs with potential immunologic etiology are outlined in Table 3 and Section 5.4.1. For each

AE, attempts should be made to rule out other causes, including but not limited to metastatic disease or bacterial or viral infection, which might require specific supportive care.

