9.2.2. Adverse Events of Special Interest

The number of participants who experienced TEAEs of special interest listed below will be summarized by maximum severity.

- Colitis
- Diarrhea
- Exfoliative dermatitis

- Febrile neutropenia
- Rash
- Intestinal perforation
- Pneumonitis
- Pneumonia
- PJP infection
- CMV infection
- Herpes simplex
- Varicella zoster virus infection

The time to onset of a TEAE is defined as the interval between the date of first dose of study drug and the date of the first occurrence of a TEAE. Participants who have not experienced a TEAE at the time of analysis will be right-censored at the earlier of 30 days after the last dose date and date of last study visit through the end of safety follow-up. If participants have missing or partial last dose dates of study drug or onset date of a TEAE, the partial or missing dates will be handled using the rules explained in Section 4.1.4.

Summaries of time to onset of new or worsening Grade 3 or higher AEs will be provided using descriptive statistics and the life-table method for rash, colitis, diarrhea, febrile neutropenia, pneumonia, herpes simplex, and varicella zoster virus infection. In addition, summaries of time to onset of new or worsening AEs of any grade will be provided using descriptive statistics and the life-table method for colitis, diarrhea, exfoliative dermatitis, intestinal perforation, pneumonia, pneumonitis, PJP infection, CMV infection, herpes simplex, and varicella zoster virus infection. Kaplan-Meier plots of time to onset of new or worsening Grade 3 or higher AEs will be provided for rash, colitis, and diarrhea. In addition, Kaplan-Meier plots of time to onset of new or worsening AEs of any grade will be provided for colitis and diarrhea.

Descriptive statistics of time to onset of these TEAEs of special interest are based on all participants who have experienced a TEAE at the time of analysis. To summarize these TEAEs of special interest using the life-table method, the effective sample size is defined as the number of participants at the beginning of the interval minus half the participants censored in the interval. The conditional proportion is calculated as the number of first events divided by the effective sample size in the interval.

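### AE-related discontinuation, the outcome the maintenance regimens are meant to reduce, is summarised by regimen in maintenance only as a crude percentage, which unequal follow-up and the Crossover rule can distort in either direction

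*SAP*

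**What the plan says.** **Purpose.** Protocol 1.5 says that "these regimens are proposed to assess whether the frequency of AEs leading to treatment withdrawal will be reduced" while response is maintained. The motivation is in Protocol 1.4: "among all evaluable subjects with an objective response (n = 20), 7 subjects (35%) discontinued study treatment due to an AE". Protocol 1.3 gives the figure for everyone treated in the earlier study: "Fourteen (19%) of the 72 subjects discontinued study treatment due to the following 14 AEs". It adds that all but one of these events came after the 9-week disease assessment, and Protocol 5.4.4 notes that "most irAEs occur after the first 9 weeks of study treatment administration". The period that matters for this aim is therefore mainly maintenance.

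**Planned measure.** SAP 9.2.3: "Overall summaries of TEAEs by treatment regimen will be provided during the INCB050465 initial QD dosing period, maintenance dosing period, and overall period". The item for this outcome is "Number (%) of participants who permanently discontinued INCB050465 because of TEAEs". For detail by term: "The following supporting summaries will be produced for TEAEs during the INCB050465 initial QD dosing period and the maintenance dosing period by MedDRA term". These are frequency tables, one of them for discontinuation by system organ class and preferred term. Neither SAP 9.2 nor Appendix A lists an exposure-adjusted rate or a time-to-event summary of AE discontinuation.

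**Time at risk.** The initial period is nominally 8 weeks in both regimens (Protocol Table 4). After it, treatment runs until progression, death, unacceptable toxicity or withdrawal of consent (SAP 3). In Cohort 2 the first 60 participants are split between A and B, and the 40 additional ones go to the selected regimen only. SAP 11.2 (Amendment 1) records that this was B.

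**Switchers.** Under SAP 5.2 and 9.2.3, a participant who switches after maintenance has started appears in a separate Crossover group in the maintenance-period safety tables.

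**The concern.** A crude percentage answers the question about withdrawals only if the groups had similar time at risk. Here three things can change it with no difference in the hazard of stopping for an AE:

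- **Calendar follow-up.** Later Cohort 2 participants, all in B, have less follow-up at a given data cutoff.
- **Progression.** A participant who leaves for progression can no longer leave for an AE, so a regimen with more progression shows fewer AE withdrawals.
- **The Crossover rule.** Participants can switch only if they are still on A when switching becomes possible. Removing them leaves an A group enriched for people who had already left, including those who left for AEs.

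The first two lower the percentage in the group with less time at risk. The third raises it in A. A reader of the maintenance tables could not tell which effect dominates. At stake is the descriptive answer to the safety aim that justifies the regimens.

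**Working it through.** **The plan's own figures.** 7/20 = 35.0%, as stated; 14/72 = 19.4%, stated as 19%. Both are crude percentages.

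**Assumed inputs.** The documents give no hazards. Let *a* be the monthly hazard of AE discontinuation, *p* that of progression, and *T* the months of maintenance follow-up, with both hazards constant. Base case: *a* = 0.03, *p* = 0.05.

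A rough check on *a* uses 14 events in 72 subjects with median treatment of 123 days (Protocol 1.3), which is 123/30.44 = 4.04 months:
- Mean taken as the median: 14/(72 × 4.04) = 0.048 per month.
- Exponential durations: 14/(72 × 4.04/ln 2) = 0.033 per month.

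Those subjects were on other doses and schedules, so this supports only the order of magnitude.

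**Formulas.** Crude percentage F(T) = a/(a+p) × [1 − exp(−(a+p)T)]. Mean exposure E(T) = [1 − exp(−(a+p)T)]/(a+p). Their ratio is *a* in every case.

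**1. Unequal follow-up, same hazards.** a/(a+p) = 0.03/0.08 = 0.375.
- T = 6: 0.375 × (1 − e^−0.48) = 14.3%
- T = 12: 0.375 × (1 − e^−0.96) = 23.1%
- T = 24: 0.375 × (1 − e^−1.92) = 32.0%

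**2. Unequal progression, same AE hazard, T = 12.**

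| *a* | *p* = 0.05 | *p* = 0.10 |
|---|---|---|
| 0.02 | 16.2% | 12.7% |
| 0.03 | 23.1% | 18.2% |
| 0.05 | 34.9% | 27.8% |

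The gap is 3.5 to 7.1 points. The exposure-adjusted rate is equal within each row (2.0, 3.0 and 5.0 per 100 person-months).

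**3. Crossover rule, same hazards in A and B, T = 12.** Half of those still on A at month *x* are moved out, independently of AE risk. With S = exp(−0.08x):
- Fraction left in A: 1 − S + 0.5S
- AE discontinuations in A: F(x) + 0.5S × F(12 − x)

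For x = 3: S = 0.787, F(3) = 0.080 and F(9) = 0.192. The fraction left is 0.607 and the events are 0.080 + 0.393 × 0.192 = 0.156. The crude percentage is 0.156/0.607 = 25.7%.

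| Switch month | A crude | A mean exposure (months) | A rate per 100 person-months |
|---|---|---|---|
| 3 | 25.7% | 6.6 | 3.9 |
| 6 | 27.1% | 6.4 | 4.3 |
| 9 | 28.0% | 6.4 | 4.4 |
| B, no switching | 23.1% | 7.7 | 3.0 |

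A has the shorter exposure and the higher percentage. A rate computed after removing switchers is biased as well (true value 3.0).

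**4. Keeping switchers in A until the switch (x = 3).** Person-time is E(3) + 0.393 × E(9) = 2.667 + 0.393 × 6.416 = 5.19 months per starter. The rate is 0.156/5.19 = 3.0 per 100 person-months, or 36 per 100 person-years, so the true value is recovered.

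**The case against.** **Time-to-event safety analyses are planned.** SAP 9.2.2 has right-censored life tables for selected adverse events of special interest, with Kaplan-Meier plots for rash, colitis and diarrhea. SAP 9.3.4 does the same kind of analysis for ALT, AST and neutrophils, and SAP 6.4 tabulates treatment duration by period. This stands: it would be wrong to infer that the SAP offers only crude percentages for safety. Life-table intervals after Week 8 do describe maintenance time. But none of these analyses covers AE discontinuation. Their clock is "the interval between the date of first dose of study drug and the date of the first occurrence of a TEAE", so it includes 8 weeks of the same starting dose in both regimens, and SAP 9.2.3 lists them for the overall period only. Tabulated exposure shows an imbalance without adjusting for it.

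**No comparison is planned.** SAP 3.2 and 5.2 exclude statistical comparison of the regimens, the safety objective is descriptive, and B had already been selected. This also stands, and it limits the consequence to interpretation.

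**Follow-up may be less unequal than assumed.** Cohort 1 closed at about 50 participants, so the expansion affects only Cohort 2. SAP 7.3 times the primary analysis at about 12 months after first response in responders, which makes 6 months of maintenance follow-up a severe case. For 12 versus 24 months the contrast is 23.1% versus 32.0%. The documents fix neither pair.

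**Cumulative incidence alone is not a cure.** F(T) in the working is itself the cumulative incidence with progression as a competing event, so it would return 23.1% versus 18.2% again in case 2. This is correct, and it is why the rate must stand beside it.

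**Conclusion.** The gap is specific. The outcome the maintenance regimens are meant to reduce has no follow-up-adjusted summary by regimen in maintenance, and SAP 9.2.3 does not state the maintenance denominator. At equal AE hazards, the illustrations give distortions of about 2.6 to 9 points, of either sign. They rest on constant assumed hazards, on half of those still on A switching, and on switching unrelated to AE risk. The A:B allocation ratio is not given, so no group sizes are assumed.

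A reader might infer that the regimen with shorter exposure will look safer. The documents do not support a fixed direction. That holds when exposure is cut by progression or data cutoff. It reverses under the plan's own Crossover rule, and also when AEs themselves shorten exposure: with *a* = 0.03 versus 0.06 and *p* = 0.05 over 12 months, the crude figures are 23.1% and 40.0%. Nor do these tables decide the regimen. The point concerns how a stated safety aim will be read, and leaves the primary efficacy analysis untouched.

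**What to change.** In SAP 9.2.3 and Appendix A, for participants who start maintenance:

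1. Add, by regimen, the exposure-adjusted rate (first events per 100 person-years of maintenance) for TEAEs leading to discontinuation and for Grade 3 or higher TEAEs. Keep switchers in their original regimen up to the switch and censor them there. Show post-switch time separately.
2. Add cumulative incidence of AE discontinuation from first maintenance dose on the same basis, with other discontinuation reasons as competing events. This handles unequal follow-up at the cutoff but not different progression rates, so report it beside the rate.
3. State the maintenance denominator, and keep the crude percentages.

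The cost is a few extra descriptive tables. Period dates are already derived for SAP 6.4 and discontinuation reasons are already collected (Protocol 5.5.2, SAP 6.2), so no new data are needed. Two limits should be noted in the SAP: the rate assumes a roughly constant hazard, and censoring at the switch assumes that switching is unrelated to the risk of stopping for an AE.

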9.3. Clinical Laboratory Tests

9.3.1. Laboratory Value Definitions

Laboratory values and change from baseline values will be summarized descriptively by visit. Baseline will be determined according to Section 4.1.3. If there are multiple values that meet the criteria for baseline, the value from the central laboratory has priority over the value from the local laboratory. Thereafter, additional rules may be provided after consultation with the medical monitor to delineate which value will be defined as baseline.

Laboratory test values will be assessed for severity based on the numerical component of CTCAE v4.03.

9.3.2. Laboratory Value Summaries

All test results and associated normal ranges from central laboratories will be reported in SI units. Any laboratory test results and associated normal ranges from local laboratories will be converted to SI units.

When there are multiple laboratory nonmissing values for a participant's particular test at a scheduled visit, central laboratory values have higher priority over local laboratory values. If a tie still exists, the laboratory value with the smallest laboratory sequence number will be used in by-visit summaries.

Numeric laboratory values will be summarized descriptively in SI units, and non-numeric test values will be tabulated when necessary. In addition, line graphs will be provided for ALT, AST, hemoglobin, platelet counts, leukocytes, neutrophils, and lymphocytes.

Shift tables will be presented showing change in CTCAE grade from baseline to worst grade postbaseline. Separate summaries for abnormally high and abnormally low laboratory values will be provided when the laboratory parameter has both high and low grading criteria. The denominator for the percentage calculation will be the number of participants in the baseline category. The number of participants who experienced worsening of laboratory abnormalities will be summarized by maximum postbaseline severity.

